### **SUMMARY**

A prospective, randomized, single-blinded clinical trial is proposed to compare Stryker Orthopaedics N2Vac Polyethylene to their X3 Polyethylene when used with the Triathlon Posterior Stabilized (PS) total knee system. This is a fixed-bearing knee intended for use in patients undergoing cemented total knee arthroplasty. The devices to be used are both FDA approved via 510k clearance.

A total of 572 cases (286 per group) will be entered. Each patient will be assessed preoperatively and post-operatively at three months and two, five, seven and ten years. The primary endpoint will be the revision rate at ten years. This outcome will be evaluated using event rates analysis assuming a Poisson distribution. Additional endpoints, including the instance of mortality, revision surgery, deep vein thrombosis, pulmonary embolus, neurovascular complication, and infection will be evaluated in the same manner. Other outcome measures incorporated in the Knee Society Clinical rating scale will undergo appropriate generalized linear regression for the type of outcome involved.

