## Hospitalization

Patients will be admitted to the hospital on the day of their surgery, unless medical problems dictate earlier admission. Hospitalization of 3 to 5 days is routine for these

patients, although complications may prolong this. These will be recorded on the data collection forms. An extension splint will not be used following surgery and no pillows are to be used under the knee. Continuous passive motion will be used according to the individual surgeon's discretion as part of the postoperative management. The patient will receive one preoperative dose and two postoperative doses of IV antibiotics separated by a 6 to 8 hour period. All patients will receive appropriate anticoagulation for deep venous thrombosis prophylaxis at the individual surgeon's discretion.

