#### **RISKS**

Participation in this study, involving FDA-approved devices, poses no increased risk to patients undergoing total knee replacement surgery. With any knee replacement, there is a possibility that the prosthesis will need to be removed and replaced and that the procedure may involve unforeseeable risks. Some of the known risks include: failure to achieve firm attachment of the implant to the bone, fracture of bone during implantation, infection, deep vein thrombosis, neurovascular injury, wound problems, extensor mechanism problems, and anesthetic problems. In a minority of cases, the knee prosthesis will loosen over years of use and pain and decreased mobility will occur.

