#### STATISTICAL METHODS AND REVIEW STATEMENT

#### **Primary Efficacy Parameters**

The primary efficacy parameter is the revision rate for total knee arthroplasty. The key time point is ten years post-surgery.

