# **Statistical Methodology**

#### **Data Summary**

All data entry and analysis will be done by the Mayo Clinic Division of Biostatistics.

The following is a detailed proposal of statistical analyses planned for data collected during the study. In general, data will be summarized by treatment group and nominal study visit, where applicable.

For parameters represented by continuous variables (e.g., ROM), the summaries will consist of the mean, median, standard deviation, minimum, and maximum values. Both the actual values at each nominal visit and the improvement from baseline at each post-baseline visit for each treatment group and their difference will be presented with its 95% confidence intervals. The improvement from baseline will also present the corresponding paired t-test p-values.

For categorical variables (e.g., subsidence), the number of events, person-years of follow-up, and the corresponding event rates with 95% confidence intervals will be presented.

In addition, the rate ratios (relative risk) of the treatment groups along with 95% confidence intervals will be presented.

Descriptive statistics and statistical comparisons for important demographic, efficacy, and safety variables will be provided in tables. All data collected on the case report forms will be provided in data listings, which will be sorted by treatment group and patient number.

Documentation of statistical analyses will be provided in a statistical appendix. All statistical analyses will be completed using SAS®, version 9 or higher (SAS Institute Inc,

Cary, NC), and Splus, version 7 or higher (Insightful Corporation, Seattle, WA).

All statistical tests will be two-sided and p-values less than 0.05 will be considered

significant.

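### DVT, PE and neurovascular complication are assigned to the Poisson person-time analysis used for ten-year revision, with no operative window or attribution rule (minor; cheap to improve)

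*Combined protocol and SAP*

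**What the plan says.** The Summary names revision at ten years as the primary endpoint and says of it: "This outcome will be evaluated using event rates analysis assuming a Poisson distribution". It then says that further endpoints, among them "deep vein thrombosis, pulmonary embolus, neurovascular complication, and infection will be evaluated in the same manner". Under Primary Efficacy Parameters, "The key time point is ten years post-surgery". For categorical variables, the Data Summary section says that "the number of events, person-years of follow-up, and the corresponding event rates with 95% confidence intervals will be presented".

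Elsewhere the plan treats these events as belonging to the operation. The RISKS section lists among the known risks of knee replacement "infection, deep vein thrombosis, neurovascular injury, wound problems, extensor mechanism problems, and anesthetic problems". Under Hospitalization, "All patients will receive appropriate anticoagulation for deep venous thrombosis prophylaxis at the individual surgeon's discretion".

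Patients are "assessed preoperatively and post-operatively at three months and two, five, seven and ten years", so the first scheduled post-operative contact is at three months.

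The statistical section does not name DVT, PE or neurovascular complication. Its safety parameters are patellar events (primary) and all other device-related adverse events (secondary). The sentence on safety analyses, printed under Modified Intent to Treat, says that they follow the method for the categorical secondary parameters. Efficacy Analyses has those analysed at every nominal visit, and Secondary Efficacy Hypothesis frames the risk as running from surgery to the visit.

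**The concern.** Revision accrues over the life of the implant, and the sample size section assumes a roughly constant 0.5% per year, so events per person-year is a natural summary. Operative complications behave differently: the risk is concentrated soon after surgery. Dividing them by up to ten years of follow-up gives an annual rate that is far too low for the post-operative weeks and has little to do with the implant afterwards. A reader of a published rate per 100 person-years could misjudge the early risk.

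There is a second, conditional issue. Entry is allowed to age 85. Without an attribution rule, a clot many years after surgery could be counted with one in the first week. Late events that are equally common in both arms would pull the rate ratio toward 1.

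**Working it through.** **The plan's own figures.** None is given for DVT, PE or neurovascular complication. The sample size concerns revision only: 26/0.05 = 520, and 520 × 1.10 = 572, or 286 per arm. These reproduce. Only the 286 and the 10% loss are used below.

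**Assumptions, not in the documents.** Operative risk p of 1%, 2% or 3%; background rate b of 0.1%, 0.2% or 0.3% per year; mean follow-up 9 years; operative window three months (0.25 year).

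**Step 1: absolute rate.** Per arm, operative events = 286 × p, late events = 286 × 9 × b, and person-years = 286 × 9 = 2574. At p = 2% and b = 0.2%:
- Operative events: 286 × 0.02 = 5.72. Late events: 2574 × 0.002 = 5.15.
- Whole follow-up: 100 × (5.72 + 5.15)/2574 = 0.42 per 100 person-years.
- First three months, operative events only: 100 × 5.72/(286 × 0.25) = 8.0 per 100 person-years.
- 8.0/0.42 is about 19.

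Over the full grid of assumptions the ratio of the two rates runs from about 10 to 28.

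**Step 2: the same check with the plan's 10% loss and no late events.** If loss occurs at a constant rate over ten years, person-years per arm are 71.4 to three months and 2714.5 to ten years, and 2714.5/71.4 = 38. An operative risk of 2% then gives 8.0 per 100 person-years to three months and 0.21 to ten years.

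**Step 3: between-arm ratio, no late events.** With equal person-time T in each arm, a true early ratio of 2.0 gives (2 × 286p/T)/(286p/T) = 2.0, whatever T is. Unequal loss matters little: 5% against 15% shifts the ten-year person-time ratio by about 6%.

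**Step 4: between-arm ratio if late events are counted.** Observed ratio = (2 × operative + late)/(operative + late), with late events equal in both arms.

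| p | b per year | Operative | Late | Late share, lower-risk arm | Observed ratio |
|---|---|---|---|---|---|
| 3% | 0.1% | 8.58 | 2.57 | 23% | 1.77 |
| 2% | 0.2% | 5.72 | 5.15 | 47% | 1.53 |
| 1% | 0.3% | 2.86 | 7.72 | 73% | 1.27 |

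**Step 5: does the plan already supply an early window?** The safety sentence, Efficacy Analyses and Secondary Efficacy Hypothesis together give a cumulative analysis from surgery to each visit, including three months. That chain reaches DVT, PE and neurovascular complication only through the secondary safety parameter, which is limited to device-related events. The complications form lists embolism as a possible complication, but neither DVT nor neurovascular injury. The Summary's own list carries no device-related limit. Coverage is therefore undetermined. Even where the chain applies, the Data Summary output is a person-time rate, not a proportion of patients, and no visit is marked as the relevant one.

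**The case against.** The strongest case on the other side has five parts.

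- **A three-month comparison may already be planned.** If these events fall under safety, the visit-by-visit rule supplies it. This stands as a possibility. A reader might infer that the plan offers only a ten-year average; the documents do not support that. They also do not settle that the events are covered.
- **The Summary may carry over only the Poisson model, not the ten-year horizon.** This is a fair reading, but it still leaves the window unstated.
- **Person-time averaging does not bias the randomised comparison.** Correct, as Step 3 shows. The absolute rate can also be unpicked from the reported counts and person-years, provided event dates are known. The absolute figure still matters, because the Secondary Safety Hypothesis compares device-related adverse events with other commercially available knees rather than between arms.
- **Counting late unrelated events is an inference.** Correct. A reader might conclude that late clots will be mixed in and the ratio diluted. The Summary would permit that, but the device-related limits on the complications form and on the secondary safety parameter may prevent it.
- **Little hangs on it.** Both arms have the same cemented operation and similar post-operative care, and the documents give no reason to expect an early difference. With 286 per arm and a true ratio of 2.0 from base risks of 1% to 3%, Fisher's exact test has about 8% to 34% power; 6 against 12 events gives p = 0.23. This stands, and it is why the point is minor.

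**Conclusion.** The point holds as a minor one. The Summary assigns three operative complications to a person-time Poisson analysis, and no section states their window or attribution rule or says whether they are device-related. A rate over the whole follow-up would describe no period of the patient's risk: 0.42 against 8.0 per 100 person-years in the central illustration. Dilution of the between-arm ratio, from 2.0 to about 1.3 to 1.8, is conditional on late unrelated events being counted. All these sizes rest on event risks assumed for illustration; the documents give none. The primary endpoint and the sample size are unaffected.

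**What to change.** In the Summary, and carried into Secondary Safety parameters and the safety-analysis sentence under Modified Intent to Treat:

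- Name DVT, PE and neurovascular complication, and say whether they count only when judged device-related.
- Analyse the proportion of operated patients with at least one such event from surgery to the three-month visit, by arm, with the difference in proportions and an exact or score 95% interval.
- List later events separately by arm, with time since surgery.
- Confirm that the complications form captures these events, with dates, whether or not they are device-related.

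No change is asked for infection or death.

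The three-month visit already exists, so if the form already captures the events and their dates the cost is wording only. If it does not, the form needs a small addition. The downside is that late DVT, PE and neurovascular events are listed rather than tested.

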#### **PURPOSE**

The primary aim of the study is to compare the survivorship of two types of polyethylene (conventional N2Vac and highly cross-linked X3) used in a fixed-bearing total knee system in patients undergoing cemented total knee arthroplasty. These results will be measured through radiographs at each post-operative interval with an independent radiograph review being performed after all patients have reached 7 and 10 year follow-up. Secondary results will also be collected and will focus on disease-specific (Knee Society Scores), global (SF-12), and outcome measures. Radiographic results consisting

of standing anteroposterior, lateral and Merchant views of the surgical knee will be recorded and analyzed. Completion of the initial investigation will occur at the 10-year interval after the last enrolled patient.

### **INTRODUCTION**

Pain, weakness, instability, and progressive dysfunction are the hallmarks of arthritis of the knee. Total knee replacement may frequently be the only therapeutic intervention to provide adequate improvement in pain and function. Fixed bearing knees have a long track record of clinical success but the issue of polyethylene wear resulting in debris that leads to osteolysis has been the limitation of the survivorship of these implants. Highly cross-linked polyethylene has been used in hips for over 7 years with excellent clinical results. However the use of first-generation of highly cross-linked polyethylene in the knee has been avoided over concerns of the ability of highly cross-linked polyethylene to withstand shear forces across the tibia.

### **METHODS AND MATERIALS**

### **Study Design**

This will be a prospective, single-blinded, randomized clinical trial. A physician's assistant will supervise the running of the study and evaluate the patients. The randomization will be provided through a password-protected computer program developed by Mayo Clinic Division of Biostatistics personnel that can be accessed at any surgical computer terminal by the research assistant. Patients will be blinded as to which

polyethylene tibial insert and patella they have received, provided they do not insist on being informed, or unless it becomes medically necessary to do so.

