### **Randomization of the Study Patients**

In order to assign patients to specific treatment groups in an unbiased manner, randomization will occur prior to surgery. After the patient has met the entrance criteria, and given full informed consent to participate in the study, they will be assigned to the treatment group. The randomization will be stratified by variables with potential confounding effects on the outcomes of interest. Specifically, patients will be stratified by gender (male / female), Body Mass Index category (<25.0 / 25.0-29.9 / ≥30) and age group (21-55 / 56-85). Within each stratum, subjects will be assigned to one of the two treatment groups using a computerized dynamic allocation program. Patient randomization will be performed just prior to surgery.

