# **Radiographic Parameters**

Standing alignment, lateral, and Merchant (45 degrees of flexion) radiographs will be obtained preoperatively, immediately postoperatively, and three months, two years, five years, seven years, and ten years after surgery. An independent reviewer will evaluate the radiographs for radiolucent lines, component position and alignment after all patients have completed the seven-year and ten-year visit.

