### **Study Procedures**

Data Collection (obtained via a blinded research assistant)

Visit #1 Preoperative: Consent and initial data acquisition: Knee Society Clinical Rating Score, SF-12, Radiographs of the knee (standing alignment, lateral and Merchant view at 45° of knee flexion)

Visit #2 Three months: Radiographs of the knee (standing alignment, lateral and Merchant view at 45° of knee flexion); Knee Society Clinical Rating Score, SF-12. These questionnaires can be obtained in-office, by phone or by mail. While it is preferred that the visit occur in the clinic, if the participant is not returning they will still be asked to complete the study questionnaires.

Visit #3

Two years: As above #2. These questionnaires can be obtained inoffice, by phone or by mail. While it is preferred that the visit occur in the clinic, if the participant is not returning they will still be asked to complete the study questionnaires.

Visit #4

Five years: As above. These questionnaires can be obtained in-office, by phone or by mail. While it is preferred that the visit occur in the clinic, if the participant is not returning they will still be asked to complete the study questionnaires.

Visit #5

Seven years: As above. These questionnaires can be obtained in-office, by phone or by mail. While it is preferred that the visit occur in the clinic, if the participant is not returning they will still be asked to complete the study questionnaires.

Visit #7

Ten years: As above. These questionnaires can be obtained in-office, by phone or by mail. While it is preferred that the visit occur in the clinic, if the participant is not returning they will still be asked to complete the study questionnaires.

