### Recruitment

The investigator or the research assistant will carry this out. The study will be described to the patient in detail, and a consent form, clearly stating the background and reasoning, will be given to the patient. A consent form will be signed by the patient and by a study person authorized to obtain consent. One copy will be go with the participant as stated, a second copy will go into the patient's medical record, and the original consent will be kept in the patient's study folder.

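### Assessor blinding is asserted once but is not secured by, and appears inconsistent with, the staff roles set out under Study Design

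*Combined protocol and SAP*

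**What the plan says.** Study Design opens with the level of blinding: "This will be a prospective, single-blinded, randomized clinical trial". The only people that section describes as blinded are the patients ("Patients will be blinded as to which" insert and patella they received), with exceptions for patients who insist on knowing and for medical need.

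The same section assigns two staff roles. On evaluation: "A physician's assistant will supervise the running of the study and evaluate the patients". On allocation, the randomization program is one "that can be accessed at any surgical computer terminal by the research assistant". Randomization of the Study Patients fixes the timing: "Patient randomization will be performed just prior to surgery".

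Study Procedures introduces the visit schedule with "Data Collection (obtained via a blinded research assistant". This is the only place where anyone other than the patient is called blinded.

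Recruitment uses the same job title again: "The investigator or the research assistant will carry this out".

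**The concern.** Whoever opens the program just before surgery learns which polyethylene the patient will receive. The job title given that access is also the one called blinded when outcomes are collected. A second member of staff, the physician's assistant, evaluates patients with nothing said about blinding.

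What is at stake is the set of outcomes that depend on a person measuring or examining. Secondary Efficacy Parameters lists active and passive flexion and extension, and the KSS pain and motion scores. Secondary Efficacy Hypothesis tests them for non-inferiority, with limits of 10 degrees for ROM and 10% for KSS. In a non-inferiority comparison, an assessor who knows the insert and leans towards the newer material would make the favourable conclusion easier to reach. The plan itself records an expectation in that direction: Sample Size Justification cites a wear reduction of up to 68% with X3. Patient blinding is conditional, so blinding of the assessor is a safeguard worth having.

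**Working it through.** No arithmetic applies, because the point depends on no rate, margin, power or sample size. The check is to set side by side every section that mentions blinding, the two assistants or outcome assessment.

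| Section | Role | Task | Blinding stated? |
|---|---|---|---|
| Study Design | Research assistant | Can open the randomization program | No |
| Study Design | Physician's assistant | Supervises the study, evaluates patients | No |
| Recruitment | Research assistant (or investigator) | Recruits | No |
| Study Procedures | Research assistant | Collects the visit data | Yes |
| Radiographic Parameters | Independent reviewer | Reads radiographs | No |
| Measurement Tools, SF-12 | Patient | Completes the form unaided | Yes, with exceptions (Study Design) |

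1. *Does one job title carry both allocation access and blinded data collection?* Yes. Study Design gives the first and Study Procedures the second.

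2. *Does any section split the title between two people?* No. There is no mention of a second research assistant, of separate log-ins, or of keeping the data collector away from the program or the operative record.

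3. *Do the documents say that one individual does both tasks?* No. This remains open.

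4. *Is it settled who scores the examined outcomes?* No. Study Design has the physician's assistant evaluate patients, while Study Procedures has the research assistant collect the data. ROM is not listed as a separate item in the visit schedule, so who measures it has to be inferred.

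5. *Which outcomes are exposed?* ROM needs a measurer, and so do the examined items of the KSS. The SF-12 is completed by the patient. Revision, the primary endpoint under Primary Efficacy Parameters, is a recorded event and not a rating by the data collector.

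From 1, 2 and 4, the blinding asserted in Study Procedures has no mechanism behind it and sits badly with the roles in Study Design. From 3, the text does not establish that the blinding is actually lost.

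**The case against.** The strongest reply is that a reader might infer that assessor blinding fails outright, and the documents do not say so. Study Design refers to the research assistant who may open the program. Study Procedures refers to a blinded one, and that adjective can be read as marking a different person. Permission to open a program is also not a statement that the same person later assesses the same patients. This part of the reply stands: a shared job title is not proof of a shared individual.

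The trial also calls itself single-blinded and describes the blinding of patients. A physician's assistant of unstated status does not contradict that label, and evaluating patients is not tied to scoring any named endpoint. That is fair as far as the label goes. It does not answer Study Procedures, which goes beyond the label and claims a blinded data collector.

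Finally, exposure is limited. The KSS section lets the questionnaires be completed in clinic, by telephone or by post, so not all KSS data pass through an examiner. Radiographs go to someone else: "An independent reviewer will evaluate the radiographs for radiolucent lines, component position and alignment". That reader's own blinding is not stated, but the reader is not part of the conflict between roles. These limits stand. They narrow the point to in-person ROM and examined KSS items, and leave the inconsistency in place for those.

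**Conclusion.** The point holds in a limited form. Blinding of the outcome assessor is asserted once, is not secured by the roles in Study Design, and appears inconsistent with them. The consequence is conditional: if the staff who can see the assignment also score outcomes, ROM and the examined KSS items are open to assessor bias. These are secondary outcomes. The primary endpoint is less exposed, although the documents do not say whether those who decide on revision are blinded. The inconsistency should be corrected because the remedy is cheap and delivers what Study Procedures already claims.

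Two further inferences are tempting and unsupported:

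- *A size in degrees.* A reader might want to set a likely bias against the 10-degree ROM limit. The documents give no figure for such a bias, nor any evidence of its direction beyond the stated expectation for X3, so no size can be given.
- *Predictable allocation.* A reader might infer that an assistant who recruits and opens the program could guess the next assignment within small strata. The stratification gives 2 × 3 × 2 = 12 strata, an average of 572 / 12 ≈ 48 patients each. The documents give no stratum counts, do not say whether the dynamic allocation has a random element, and do not say that the assistant sees past assignments. Predictability cannot be judged from them.

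**What to change.** - In Study Design, give access to the randomization program to existing theatre staff who neither recruit, judge eligibility nor score outcomes. They handle the assigned insert anyway. Access for the operating surgeon is less suitable, because Recruitment lets investigators recruit and Eligibility Criteria has the surgeon investigator judge the collateral ligaments.
- Bar the research assistant who collects outcomes from the program and from operative records that name the insert.
- Reconcile Study Design with Study Procedures: state that ROM and KSS scoring is done only by that blinded assistant, and that the physician's assistant supervises and does not score outcomes unless also kept blinded.

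The cost is a change of log-in rights and a few sentences. The small downside is that theatre staff must do the look-up just before surgery. That this needs no extra staff is an assumption, since the documents give no staffing information. No sample size, power or alpha figure changes.
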